CLINICAL STUDY PROTOCOL

VERSION 2.1 (APRIL 2021)

STUDY SUMMARY

Full Title: A Randomized Controlled Trial of Online Cognitive

Behavior Therapy for Insomnia (CBT-I) and Perceived

Cognitive Impairment (PCI) in Cancer Survivors

Short Title: Online CBT-I for PCI

Clinical Trials Information NCT04026048

Principal Investigator: [name]^{1,2}

Co-Investigators: [name], PhD¹

[name], FRCP²

[name], PhD³

[name], PhD⁴

[name] FRCPC²

[name], FRCP²

Patient Co-Investigator: [name]

Affiliations: ¹ Department of Psychology, MUN Faculty of Science

² Division of Oncology, MUN Faculty of Medicine

³ Département d'école de psychologie, Université Laval

⁴ Department of Community Health and Epidemiology, Faculty

of Medicine, Dalhousie University

Sponsor: Canadian Institutes of Health Research (CIHR)

Title	A Randomized Controlled Trial of Online Cognitive Behaviour Therapy for Insomnia (CBT-I) and Perceived Cognitive Impairment (PCI) in Cancer Survivors						
Short Title	Online CBT-I for PCI						
Protocol Number	HREB Application Ref No: 12843; ClinicalTrials.gov Identifier: NCT04026048						
Phase	Phase IV						
Methodology	Randomized controlled trial						
Study Duration	4 year						
Study Center(s)	Memorial University of Newfoundland (MUN)						
Objectives	Primary Objective: 1: To examine whether treating insomnia using online CBT-I improves PCI in cancer survivors compared to a waitlist control group. Secondary Objectives: 1: To determine whether treating insomnia using online CBT-I can improve objective cognitive function at the end of treatment compared to a waitlist control group. 2: To evaluate whether change in insomnia better accounts for improvements in cognition than depression, anxiety, and/or fatigue. 3: To explore whether treatment of insomnia and PCI reduces work presenteeism and absenteeism. 4: To investigate associations between subjective and objective measures of cognitive function and sleep.						
Number of Participants	130						
Diagnosis and Main Inclusion Criteria	 For individuals with non-hematological malignancies: Men and women who are easily able to understand and read English No current evidence of cancer or clinically stable/inactive disease Received and completed all adjuvant treatments at least 6 months prior to study entry to allow for neural stabilization and recovery Continued maintenance or hormonal therapies are acceptable Report PCI as indicated by a score of "quite a lot" or "always" on at least one of the two items that assess concentration and memory on the EORTC [1] 						

	 Meet the DSM-5 criteria for insomnia disorder and have a score of 8 or greater on the Insomnia Severity Index^[2] Have an ECOG score of 0-2, indicating that they can care for themselves (working, walking), have good daily activity, and good physical ability Have high-speed internet connection, webcam, and are fluent using the internet 							
	 For individuals with hematological malignancies: Men and women who are easily able to understand and read English 							
	 A diagnosis of a hematological malignancy currently in remission. 							
	 Completed cancer treatments including transplant, chemotherapy and/or immunotherapy at least 6 months prior to study entry 							
	Report PCI as indicated by a score of "quite a lot" or "always" on at least one of the two items that assess concentration and memory on the EORTC [1]							
	 Meet the DSM-5 criteria for insomnia disorder and have a score of 8 or greater on the Insomnia Severity Index^[2] 							
	 Have good performance status as indicated by an ECOG score of 0-2 							
	 Have high-speed internet connection, webcam, and are fluent using the internet 							
Study Product, Dose, Route, Regimen	Online delivered CBT-I via video-conferencing							
Duration of administration	Participants will receive seven components of online CBT-I via video- conferencing over the course of 8 weeks.							
Reference therapy	Waitlist control group							
Statistical Methodology	Primary research question data will be analyzed using mixed-effects models. Secondary research questions will be answered using mediation/moderation analyses and/or additional mixed effects models.							

1. ETHICS

The study will be approved by local research ethics boards, The Health Research Ethics Board (HREB) and the Research Proposals Approval Committee (RPAC).

The study will be conducted in accordance with the Tri-Council Policy Statement on Ethical Conduct for Research Involving Humans 2 (TCPS2) http://www.pre.ethics.gc.ca/eng/policy-policy-policy/policy-policy/policy-policy/policy-policy/policy-polic

2. OBJECTIVES OF THE STUDY

Primary Objective: To examine whether treating insomnia using online CBT-I improves PCI in cancer survivors compared to a waitlist control group.

Secondary Objectives:

- 1: To determine whether treating insomnia using online CBT-I improves objective cognitive function compared to a waitlist control group.
- 2: To evaluate whether change in insomnia better accounts for improvements in cognition than depression, anxiety, and/or fatigue.
- 3: To explore whether treatment of insomnia and PCI reduces work presenteeism and absenteeism.
- 4: To investigate associations between subjective and objective measures of cognitive function and sleep.

3. BACKGROUND, SIGNIFICANCE, AND RATIONALE

[figure not shown]
3.1 BACKGROUND: For cancer survivors, one of the biggest barriers to resuming normal functioning is perceived cognitive impairment (PCI). Approximately 75% of cancer patients report a decline in a variety of cognitive domains during chemotherapy and/or hormonal therapy, and up to 35% continue to experience cognitive difficulties for months or years post-treatment. [3] While the evidence supports the high prevalence of PCI, the research is inconclusive about how to treat these difficulties. [4] Pharmacological interventions have largely been ineffective at preventing or treating PCI. [5] The efficacy of cognitive remediation programs is also inconclusive, with some, but not all, studies reporting improved cognition. [6] Studies to date have largely ignored the possible impact of sleep, which could account for the less than impressive findings.

Sleep disturbances, primarily in the form of insomnia, are an especially important, but frequently overlooked, consequence of cancer and associated treatments.^[7, 8] Several large-scale epidemiological studies demonstrate that close to 60% of people treated for cancer experience insomnia.^[9, 10] When patients were asked about the development of their insomnia, most reported that it began with, or followed, their cancer diagnosis,^[11] and that the effects of poor sleep were more overwhelming than the effects of cancer treatment.^[12] Unfortunately, once chronic, sleep disturbances are unrelenting if not appropriately treated, and can persist for years

or even decades.^[10] Sleep difficulty is one of the most frequent reasons that cancer survivors visit their general practitioners.^[13] In Canada, annual indirect costs associated with insomnia-related absenteeism were estimated at \$970.6 million overall, with insomnia-related productivity losses estimated at \$5.0 billion.^[14] The average annual per-person costs (direct and indirect combined) were \$5,010 for individuals with insomnia compared to \$421 for good sleepers.^[14] Further, 40.6% of Canadians with insomnia reported having experienced reduced productivity compared to 12.3% of good sleepers.^[15] Sleep disturbance significantly mediates the impact of cancer on healthcare expenditures and absenteeism, suggesting that addressing sleep disturbance may result in economic benefits in addition to improvements in health and quality of life.^[16]

Disrupted sleep has negative consequences for cognition in the general population. Numerous experimental studies have demonstrated that both acute total and cumulative partial sleep loss lead to deteriorations in a wide range of cognitive functions such as sustained attention, executive function, and memory (for a review, see Banks and Dinges ^[17]). Poor sleep and insomnia are significantly associated with subjective and objective cognitive complaints in cancer populations as well. ^[18-20] Recent evidence challenges the conventional idea that the

cancer treatment itself is responsible for the changes in cognition and places sleep in the spotlight as a potent contributor.^[21] To guide the design, methods, and analyses for the proposed research, we have built a conceptual model (Figure 1) that is grounded in the current scientific understanding of how cancer and its treatment and side effects might, directly or indirectly,

*The experience of fatigue has both a physical and psychological component

contribute to sleep disturbance, which can then, alone or in combination with psychological disorders, contribute to PCI.

Cognitive Behaviour Therapy for Insomnia (CBT-I) is specifically designed for insomnia and is recommended by the American College of Physicians and the American Academy of Sleep Medicine as a first line treatment for chronic insomnia. [22, 23] CBT-I has demonstrated efficacy in several randomized controlled trials (RCTs) in the general population. [24-27] CBT-I is also the treatment of choice in the context of cancer-related insomnia. [28] Recent evidence also suggests that CBT-I has broad effects and offers concomitant improvements in fatigue, anxiety, and depression related to cancer treatment, [29] all of which have been associated with PCI. The correlation between PCI and insomnia persists more than 18 months post-diagnosis, and there is some evidence suggesting that patients with insomnia are more likely to develop PCI. [30] Moreover, preliminary evidence from secondary analyses suggests that CBT-I may improve PCI [31] but additional research is required to investigate this question a priori with more refined subjective and objective measures of cognitive functioning, controlling for other factors that may explain this effect.

[figure not shown]
Despite the advantages of CBT-I, it is underutilized for a number of reasons such as a limited number of trained CBT-I providers, poor geographical distribution of these providers, limited insurance reimbursement, and relatively high costs of face-to-face delivered CBT-I. [32, 33]. A solution to these issues and an approach to increase access to CBT-I is the online delivery of the intervention via video-conferencing platforms. The internet is increasingly being used to deliver a wide range of behavioral and mental health programs and has had excellent success. [32]

3.2. SIGNIFICANCE: Treatment of PCI in cancer patients is a priority for clinicians, researchers, and patients, making the current trial a necessity. [34] Cognitive difficulties have a direct impact on work productivity, long-term absence, retirement intentions, and early retirement. [35] The proposed study is highly significant in that it is the first RCT specifically designed to examine whether PCI in cancer survivors can be improved using the "gold-standard" non-pharmacological intervention for insomnia. [22] This research will inform our understanding of the mechanisms of cognitive impairment associated with cancer and help determine whether CBT-I could be used alone or in adjunct to other therapies (e.g., cognitive remediation) to treat PCI.

4. STUDY DESIGN

4.1. Overall Design: The proposed trial is an RCT of immediate treatment with CBT-I compared to a waitlist control for PCI in cancer survivors with insomnia (see Figure 2). Participants will receive individual CBT-I delivered by via online video-conferencing over the course of eight weeks. Participants in the waitlist control group will be required to monitor their sleep with sleep diaries for 8 weeks. They will receive CBT-I delivered by via video-conferencing immediately after the waiting period. Both groups will complete follow up assessments three and six months after completing treatment. The total study duration for the immediate and delayed treatment groups is 8 and 10 months, respectively. We chose a waitlist, or delayed treatment, control group because it would be unethical to refuse participants with insomnia the opportunity to receive CBT-I. The use of a waitlist control is also more representative of real-world health care in Canada, where patients will often have to wait for a certain amount of time before receiving treatment and will control for the regression to the mean.

Figure 2: Trial Design

5. SUBJECT SELECTION AND WITHDRAWAL

5.1. Subject Recruitment: We plan to recruit a sample of 130 cancer survivors from across the Atlantic provinces (Newfoundland and Labrador, Prince Edward Island, Nova Scotia, and New Brunswick) who completed chemotherapy and/or radiation treatment at least 6 months prior to enrollment (for non-hematological malignancies) and completed cancer treatments including transplant, chemotherapy and/or immunotherapy at least 6 months prior to study entry (for hematological malignancies). We are confident in our ability to recruit the proposed sample. Newfoundland and Labrador has the highest age standardized incidence rate for cancer in Canada. [36] All of the oncologists providing cancer care at Eastern Health (including Co-ls Drs. [name] and [name]) are highly committed to the successful completion of this study. Because we are recruiting cancer survivors at least 6 months after completion of cancer treatment, we will have a large pool of participants to draw from. The primary means of recruitment will be selfreferral; however, we will also employ creative strategies that have been successfully used in previous studies to recruit local participants including: identification of patients with sleep problems through the Personal Well-being Checklist, a distress screening initiative used by the Dr. H. Bliss Murphy Cancer Centre; posting announcements and pamphlets available in the main areas of cancer centres and other areas where eligible patients may frequent; notification of treating physicians across areas (e.g., medical oncology, radiation oncology, hematology oncology, general oncology), nurses and allied health professionals; having new patients consent to be contacted at a later date; notification of community support groups and posting of information on websites frequented by patients; media releases for local newspapers and television programs; paid advertising in print media, on the radio, television and/or internet; and posting advertisements on Kijiji, Buy and Sell, and Classifieds. A key recruitment method to ensure we can make patients across the province and Atlantic Canada aware of the study opportunity is to mail study invitation letters to patients through the Newfoundland and Labrador provincial cancer registry and the Atlantic Path study. Recruitment via the cancer registry will be conducted with the approval and cooperation of the NL Cancer Care Registry (NLCCR). Recruitment via the Atlantic Path study will be conducted with the approval and cooperation of Atlantic Path. Eligible patients (defined as any individual with no current evidence of cancer or clinically stable/inactive disease who completed cancer treatment at least 6 months ago) will be identified by registry cancer case and Atlantic Path records and mailed an invitation letter to participate in the study. The personal information of the individuals eligible for the invitation letter will not be made available to the researchers in this study. Study personnel will provide the stuffed envelopes and the registry or Atlantic Path will be responsible for mailing them, to ensure protection of privacy. Previous studies conducted by the principal investigator have seen successful recruitment through this strategy.

The mail out will include:

NLCCR:

- two letters
 - o a letter from the NLCCR
 - o a letter from the principal investigator
- two brochures
 - one about the NLCCR (http://cancercare.easternhealth.ca/wp-content/uploads/sites/2/2018/02/Cancer-Registry-NLCCR-Brochure_2017-1.pdf)
 - one about our study

Atlantic Path:

- a letter from the principle investigator
- a brochure about our study

Conservative estimates indicate that approximately 15% of patients will be both eligible and interested in participating in our research, yielding 525 potential participants per year. We aim to recruit 1-3 participants per week or approximately 5 participants per month (30 in Year 1 to allow study launch time, 58 in Year 2, and 36 in Year 3). As such, we are more than able to recruit 130 participants in the study period.

Table 1: Study Timeline

TABLE 1	YEAR 1		YEAR 2			YEAR 3			YEAR 4							
Hire/Training																
Treatment Group (n)		7	11	12	14	14	15	15	15	15	6					
Waitlist Group																
Follow Up																
Data Entry/Cleaning																
Data Analysis																
Writing/KT																

5.2. Inclusion Criteria:

5.2.1 For individuals with non-hematological malignancies:

- Men and women who are easily able to understand and read English
- No current evidence of cancer or clinically stable/inactive disease
- Received and completed all adjuvant treatments at least 6 months prior to study entry to allow for neural stabilization and recovery
- Continued maintenance or hormonal therapies are acceptable
- Report PCI as indicated by a score of "quite a lot" or "always" on at least one of the two
 items that assess concentration and memory on the EORTC [1]
- Meet the DSM-5 criteria for insomnia disorder and have a score of 8 or greater on the Insomnia Severity Index^[2]
- Have good performance status as indicated by an ECOG score of 0-2.
- Have high-speed internet connection, webcam, and are fluent using the internet

5.2.2 For individuals with hematological malignancies:

- Men and women who are easily able to understand and read English
- A diagnosis of a hematological malignancy currently in remission.
- Completed cancer treatments including transplant, chemotherapy and/or immunotherapy at least 6 months prior to study entry
- Report PCI as indicated by a score of "quite a lot" or "always" on at least one of the two
 items that assess concentration and memory on the EORTC [1]
- Meet the DSM-5 criteria for insomnia disorder and have a score of 8 or greater on the Insomnia Severity Index^[2]

- Have good performance status as indicated by an ECOG score of 0-2.
- Have high-speed internet connection, webcam, and are fluent using the internet

5.3. Exclusion Criteria:

5.3.1 For individuals with and without hematological malignancies:

- Another sleep disorder, besides insomnia, that is not adequately treated (ie: untreated obstructive sleep, sleep apnea)
- The presence of another psychological disorder that is not currently stable and/or would impair the ability to participate in the study
- A major sensory deficit (e.g. blindness)
- A neurologic or major medical condition known to affect cognitive function (e.g., Parkinson's)
- A history of cranial radiation
- A history of any other condition that may affect cognitive functioning (e.g., traumatic brain injury)
- Previous experience with CBT-I

Participants will not be excluded for using psychotropic medication prior to study entry (e.g. antidepressants) provided that the dose was not recently altered (stable over the previous 6 weeks). Considering the potential for prescription of medications to help with sleep (e.g. hypnotics, sedatives, and antidepressants) within the cancer population, medication use throughout the study will be tracked and adjusted for in the statistical analysis.

5.4. Early Withdrawal of Participants:

Any participant withdrawing their consent to participate in the study or their authorization to use their protected health information will be withdrawn from the study. Participants withdrawn may be replaced, at the discretion of the principal investigator.

Reasons why participants are withdrawn will be documented on the Study Termination Form. Every effort will be made to continue to collect data on every participant for the entire study duration regardless of whether the participant continues to complete assessments, assuming the participant has not withdrawn his/her authorization to obtain such information.

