Medical history and demographics: A medical history and demographics questionnaire will be administered at the baseline assessment. This questionnaire will be used to obtain patient demographic information (e.g., sex, age, ethnic background, education, marital status, current employment status), medical history (e.g., type of cancer, dates of diagnosis and treatment, types of treatment received), psychiatric history, and current medication use. The Credibility/Expectancy Questionnaire (CEQ)^[38] will also be used at baseline to examine possible moderators of treatment effects.

Primary Outcome - The Functional Assessment of Cancer Therapy – Cognitive Function (FACT-Cog), version 3: The FACT-Cog will be used as the measure of perceived cognitive impairment. It is a 37-item questionnaire with four cognitive subscales: perceived cognitive impairments, impact on quality of life, comments from others, and perceived cognitive abilities. [20, 39] Responses range from 0, "never," to 4, "several times a day," in the previous 7 days. A change of 10.6-points has been established as clinically meaningful change on the FACT-Cog. [39-41]

Secondary Sleep Outcomes: The Insomnia Severity Index (ISI) has 7-items designed to specifically assess the severity of insomnia symptoms, the impact on daytime functioning, and the amount of associated distress.^[2] The ISI has established minimally important change values to ensure that the change is not only statistically significant, but also clinically meaningful to patients.

The Consensus Sleep Diary (CSD) provides a night-by-night, self-report of sleep duration, disruption, and perceived quality and will be used to capture more subtle variations in sleep. The sleep diary will be used to calculate sleep efficiency, sleep-onset latency, wake after sleep onset, total sleep time, time in bed, number of awakenings, sleep quality, and terminal wakefulness. Sleep diaries are considered a reliable and valid patient report of nightly insomnia symptoms. Participants will complete the sleep diary for one week at each assessment point. However, during the COVID-19 pandemic, participants will only complete the diaries if they are able to do so electronically (print and send back electronically, or fill out on their computer and email back). Participants who require a printed copy of the diary to be mailed will not complete the sleep diary component during the pandemic.

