8.2. Data Analysis Plan

8.2.1. Analysis Plan: To answer our primary research question, we will use mixed-effects models to determine whether treated patients had greater improvements immediately post-treatment (primary endpoint) compared with patients in the control group after their waiting period. Then, data from both groups will be pooled together to assess, with a larger sample size, the durability of any effects observed at 6 months (secondary endpoint). This statistical procedure considers within-subject correlations from repeated measurements in the same subjects and allows estimation of between-group differences without necessitating last observation carried forward or exclusion of participants with missing data. Secondary and exploratory research questions will be answered using mediation/moderation analyses and/or additional mixed effects models.

The primary analyses will occur after the treatment completion (primary endpoint) and durability analyses will occur after the 6-month follow-up (secondary endpoint).

Subsidiary analyses will be conducted to examine the role of sex, gender, and sexual orientation in participant recruitment and retention, pre-treatment symptom severity, as well as the overall efficacy of online CBT-I, and results will be reported separately.

8.2.2. Missing Data: A drawback of any study is the risk of missing data and attrition bias. Our first line of defense will be to minimize the occurrence of missing observations, using a well-constructed study design, well-trained research staff, and acceptable subject burden.^[53] We will decrease barriers to recruitment/retention by scheduling study visits at a convenient time. For those who voluntarily withdraw from the study, we will record their reasons for withdrawing and use this information in a sensitivity analysis. To minimize missing data, all surveys will be checked right after completion. If needed, calls will be made to participants to complete missing data over the phone. For individuals who miss a study visit, RAs will call at least three times (morning/afternoon/evening) over the next week to try rescheduling the assessment.

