Our second line of defense is to apply data analysis strategies that are as robust as possible to data losses. [54] Seeing that no universally accepted method exists for handling missing data, we will initially perform intent-to-treat analyses. We then will perform sensitivity analyses to evaluate the robustness of our results, including compete-case analysis, single imputation methods, such as last-observation and baseline carry forward analyses, and multiple imputation analyses. To avoid reporting bias, we will register our trial with ClinicalTrials.gov and follow the CONSORT recommendations for reporting randomized trials of nonpharmacological interventions. [55]

8.2.3 Sample Size Considerations: Our sample size is based on our primary outcome of PCI using the FACT-Cog immediately post-treatment. Since the primary outcome is continuous, we powered our trial using a t-test to detect the difference between two independent means for score at post-treatment. This is a conservative way to estimate sample size since the longitudinal analysis using the mixed-effects model specified in the analysis plan will provide greater power than a t-test. With power of 0.8 and two-sided alpha of 0.05, we will need at least 62 participants per treatment group and 124 in total to detect an effect size of 0.5.

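### Section 5.3 commits the analysis to adjusting for medication use throughout the study, without limiting this to baseline use; followed in the CBT-I versus waitlist comparison, it could bias the total effect

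*Combined protocol and SAP*

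**What the plan says.** - **Section 5.3 (Exclusion Criteria).** Psychotropic medication is allowed if the dose was stable over the 6 weeks before entry. Because drugs for sleep may be prescribed in this population, "medication use throughout the study will be tracked and adjusted for in the statistical analysis". No model, endpoint or form of covariate is named.
- **Section 2 (primary objective).** "To examine whether treating insomnia using online CBT-I improves PCI in cancer survivors compared to a waitlist control group".
- **Section 8.2.1 (Analysis Plan).** The primary comparison is CBT-I against waitlist at the end of the treatment or waiting period, by mixed-effects models. No covariates are listed. For the rest: "Secondary and exploratory research questions will be answered using mediation/moderation analyses and/or additional mixed effects models".
- **Section 8.2.2 (Missing Data).** "we will initially perform intent-to-treat analyses", followed by sensitivity analyses for missing data. Covariates are not mentioned.
- **Section 7.6 (Medical history and demographics).** "A medical history and demographics questionnaire will be administered at the baseline assessment"; it covers, among other items, "psychiatric history, and current medication use". Medication use at T0 is therefore available, but the adjustment promised in 5.3 is not tied to that value.

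**The concern.** The primary objective asks for the total effect of being assigned to CBT-I rather than waitlist. Use of sleep medication during the 8 weeks after randomisation is not a baseline characteristic. Successful CBT-I may reduce it, and waiting with untreated insomnia may increase it.

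Conditioning on such a variable does two things. It removes any part of the effect that passes through medication. It can also open a path through unmeasured severity that drives both medication use and FACT-Cog. Randomisation protects the comparison from neither. Adjusting for T0 use does neither.

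The 5.3 sentence is the only text that says how medication enters any analysis, and it points to use throughout the study. One analyst could put on-study use in the primary model and another could leave it out, and both would be following the protocol. That choice should not be open once data are available.

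**Working it through.** **1. Does any text limit the rule?** Section 5.3 says adjust, for use throughout the study. Section 7.6 records T0 use but does not confine the adjustment to it. Section 8.2.1 neither includes nor excludes medication. The intent-to-treat statement in 8.2.2 settles who is analysed, not which covariates enter. So there is no limit, and no express placement in the primary model.

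**2. Planned effect, for scale only.** Section 8.2.3 plans 62 per group (124 in total) for an effect of 0.5 SD, power 0.8, two-sided alpha 0.05. Normal approximation: n = 2 × (1.960 + 0.842)² / 0.5² = 2 × 7.851 / 0.25 = 62.8, so 63 per arm. The exact t-test gives 64. Power at 62 per arm is 0.795 (normal) or 0.789 (t). The stated figure reproduces closely, and the point does not depend on it.

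**3. Size of the shift in a linear model.**

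adjusted minus unadjusted arm effect = -(medication coefficient given arm) × (use on CBT-I - use on waitlist)

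If use is equal by arm, the shift is zero. With an assumed coefficient of -0.4 SD and use of 30% against 40%: -(-0.4) × (-0.10) = -0.04 SD. At 20% against 40%: -(-0.4) × (-0.20) = -0.08 SD. With a coefficient of +0.4 SD the signs reverse.

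**4. Illustration with shared severity.** Every medication input is assumed; none is in the documents.
- Total effect 0.5 SD, with higher scores taken as better.
- T0 use 40% in both arms; T2 use 40% on waitlist.
- T2 use depends on arm, on T0 use (log-odds 2.0) and on unmeasured severity (log-odds 0 or 0.7 per SD).
- Severity loading on FACT-Cog 0, 0.3 or 0.5; T0-T2 correlation 0.45 to 0.52.
- Random-intercept model on T0 and T2 scores with time-varying medication; 2,000,000 simulated participants per scenario.

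Shift in the arm effect (SD), by T2 use on CBT-I:

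| Medication effect; severity loading | 40% | 30% | 27% | 20% |
|---|---|---|---|---|
| none; none | 0.00 | 0.00 | 0.00 | 0.00 |
| -0.4; none | 0.00 | -0.040 | -0.052 | -0.080 |
| none; 0.3 | 0.00 | -0.014 | -0.018 | -0.027 |
| none; 0.5 | 0.00 | -0.024 | -0.031 | -0.046 |
| -0.4; 0.3 | 0.00 | -0.054 | -0.070 | -0.107 |
| -0.4; 0.5 | 0.00 | -0.064 | -0.083 | -0.126 |
| +0.4; none | 0.00 | +0.040 | +0.052 | +0.080 |
| +0.4; 0.3 | 0.00 | +0.026 | +0.034 | +0.053 |
| +0.4; 0.5 | 0.00 | +0.017 | +0.022 | +0.034 |

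Adjusting for T0 use only shifts the estimate by 0.000 in all 36 scenarios.

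**5. How far this depends on the inputs.** The -0.126 extreme becomes -0.101 with ANCOVA on baseline FACT-Cog and -0.157 with the T2 score alone. A separate simulation of the post-treatment score, with use from 30% v 20% up to 40% v 10%, a medication effect of 0 to -0.5 SD and correlations of 0.5 and -0.5 with a shared cause, moves a total effect of 0.50 to anywhere between no change and 0.22. The model in step 4 also leaves out the T1 FACT-Cog score, which both arms provide. The figures show the mechanism; they do not measure a defect in this trial.

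**The case against.** The strongest reply is that the 5.3 sentence is not a model specification. It sits under the exclusion criteria and speaks only of the statistical analysis in general. The section that does specify the primary model lists no covariates. On-study medication could enter the pooled 6-month durability analysis or a secondary model without touching the randomised comparison. The only medication data collection described in detail is at baseline. Harm also needs three things together: adjustment in the primary model, use that differs by arm at T2, and medication related to FACT-Cog given arm. Doses must be stable for 6 weeks before entry, the contrast spans about 8 weeks, and the CBT-I components listed in section 6 include no medication reduction.

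Much of this stands. The documents do not show that use will differ by arm, and they do not commit the primary model to this covariate. But the entry rule does not fix use afterwards, and silence in 8.2.1 does not cancel an explicit commitment in 5.3.

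Three stronger readings are tempting, and the documents do not support them:
- That the primary model will contain on-study medication, so that the primary result will be biased. No text says so.
- That the background phrase "controlling for other factors that may explain this effect" in section 3.1 shows that medication was meant for the main comparison. The phrase describes what further research needs. Its paragraph names fatigue, anxiety and depression and does not mention medication. Those three factors return in secondary objective 2, which 8.2.1 sends to mediation or additional models. The point rests on the 5.3 sentence alone.
- That the lack of a medication row in Tables 1a and 1b means that use will not be tracked. Those tables omit the baseline questionnaire too, so the gap shows little.

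**Conclusion.** The concern holds in conditional form, with medium confidence, and should be fixed. The current text states an adjustment rule that includes post-randomisation medication use, and nothing keeps that rule out of the CBT-I versus waitlist comparison. If it is applied there, the estimate departs from the total effect whenever use differs by arm and is related to FACT-Cog given arm.

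Neither size nor direction can be obtained from the documents. On the assumed inputs of step 4 with 20% to 30% use on CBT-I, the shift lies between -0.13 and +0.08 SD. The lower end needs all the strongest assumptions at once, and other assumptions give other ranges. What does not depend on those inputs is that equal use by arm gives no shift, and that adjusting for baseline use leaves the total effect as the target.

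**What to change.** Amend 5.3 and add to 8.2.1: *As regards medication, the CBT-I versus waitlist models adjust at most for use at baseline (T0). Outcomes are analysed regardless of medication changes after randomisation. On-study medication use enters only models labelled sensitivity, exploratory or mediation.*

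The cost is three sentences. T0 use is already collected, so the primary model needs no new data, and the sample size does not change. The downside is that the primary model then gives no estimate that holds on-study medication fixed; that estimate moves to a labelled secondary model.

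A minor addition: state when on-study medication use is recorded, since 5.3 promises tracking but neither section 7.6 nor its tables give a time after baseline.
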